To explore possible causes, the principal investigator conducted end-of-semester interviews with students in the 2021 academic year. Among students in the bottom 15% of OSCE scores, the most frequently cited reasons for poor performance were nervousness, mental blanks, insufficient practice, and forgetting procedural steps. In contrast, students in the top 15% attributed their success to diligent practice, peer collaboration, error correction, and exchanging feedback (Table 2). Overall, poor performance appeared to be linked not only to insufficient practice but also to difficulties in memorizing detailed procedural steps, low learning motivation, lack of peer feedback, and low self-confidence.

Table 1. OSCE Performance in Clinical Nursing Skills I, 2019–2021 Academic Years**Academic Year Midterm Score Final Score Overall Average**

2019	70.4	52.6	61.5
2020	70.0	51.2	60.6
2021	68.2	52.3	60.25

Table 2. Experiences and Perceptions of Students in the Top and Bottom 15% of OSCE Scores

Performance Group	OSCE Perceptions	Learning Experiences
Top 15%	Nervousness, high pressure, focus on execution, avoiding distraction by teacher	Frequent practice, peer collaboration, error-sharing, attentive listening, targeted improvement on mistakes
Bottom 15%	Nervousness, mental blanks, inability to recall steps, lack of confidence	Minimal practice, unclear causes of errors, low interest, low self-confidence

Nursing skills are frequently acquired through **observational learning**, also known as modeling, whereby individuals acquire new behavioral patterns by observing and imitating the actions, attitudes, or emotional responses of others (11). This process combines generalized imitation, conditional reinforcement, and rule-governed behavior to enhance learners' self-efficacy and achieve learning goals (12). Prior studies have shown that observational learning is particularly effective in disciplines that require demonstration of procedural skills (13).

In the 21st century, shaped by rapid developments in information and communication technology (ICT), Industry 4.0, and 5G networks, students tend to process visual content more effectively than text and prefer interactive, student-centered learning environments (14, 15). Modern learning spaces should therefore employ multimodal, flexible, and ICT-based teaching strategies tailored to students' styles, interests, and needs.

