4.1. Course Design and Planning

The curriculum is aligned with the Fundamentals of Nursing course, which is structured according to Gordon's 11 Functional Health Patterns. Each week, the clinical skills course corresponds to the same week's theoretical content. The remaining five weeks cover techniques that are not directly linked to weekly theoretical content, such as vital sign measurement, medication administration, and injection techniques. Two additional weeks are allocated for skills examinations. The course content integrates theoretical and technical components. The theoretical component includes anatomy, physiology, pathology, pharmacology, health assessment, and ethical considerations related to each nursing skill, incorporating the concept of evidence-based practice. The technical component relies on instructional videos produced by faculty members, covering equipment preparation, procedural steps, and key considerations. The main reference text is the OSCE skills manual co-authored by the clinical faculty.

Teaching activities include both online and in-person sessions. Online learning allows students to independently review theoretical content and instructional videos outside of class. In-person sessions (4 hours per week) are held in the skills demonstration laboratories, where nine faculty members provide demonstrations and guided practice in small groups. Faculty members evaluate each student's performance using structured checklists, providing individualized feedback on strengths and areas for improvement.

During practice, instructors emphasize patient perspectives, encouraging students to demonstrate empathy, compassion, and communication skills. As observational learning accumulates from peer performances, later-performing students often demonstrate improved techniques. At this stage, instructors introduce potential procedural challenges, guiding students to apply critical thinking and develop problem-solving abilities. Following each class, students are provided with two hours of independent practice time in the laboratory (without instructor supervision or course credit), and they are encouraged to post questions and engage in online discussions when encountering difficulties.

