4.2. Student Assessment and Evaluation Tools

Student performance will be assessed using the following tools:

Skills Examinations: Practical OSCEs evaluating core clinical skills.

Written Examinations: Theoretical assessments through multiple-choice and short-answer questions.

Quizzes: Short tests to reinforce knowledge and monitor progress.

Independent Practice Participation: Records of students' engagement in self-directed practice sessions.

5. Research Participants and Setting

This study will be conducted in the Clinical Nursing Skills courses for second- and third-year undergraduate nursing students in the 2024–2025 academic year. The study population will include approximately 170 students (about 85 students per year, with possible attrition due to withdrawal or leave of absence).

Before class, students will engage in pre-class learning through the Moodle system, which includes theoretical principles of nursing skills and instructor-produced instructional videos, supplemented by a technical procedures manual. In the practical sessions, the SimCapture simulation-based training platform will be introduced to support course integration, management, and evaluation in a cloud-based format, thereby facilitating effective post-class learning.

All participants must complete a video-recording consent form prior to participation. Students who decline recording will be excluded from the study and will not be provided with an account or password. Video recordings will capture only hand movements to minimize facial identification. Each student will receive a unique account and password, and students will only have access to their own group's videos.

6. Research Methods and Instruments

This study will adopt an Action Research approach. Action research is a methodology designed to improve practice and address real-world problems, commonly applied in fields such as education, social sciences, and healthcare. It involves iterative cycles of problem identification and planning, action implementation, observation and reflection, and revision and re-planning. A defining feature of action research is its emphasis on practical change, participatory collaboration, and reflective practice. The implementation steps of this study are as follows:

(1) Planning the Intervention

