The research theme is defined as “designing nursing procedural instruction based on observational learning theory.” The intervention plan will be grounded in relevant literature on symbolically coded procedural steps, enhancement of learning motivation, and reinforcement of self-efficacy.

(2) Executing the Intervention

The SimCapture teaching management platform will serve as the central tool for course delivery. This cloud-based system captures audio, video, annotations, and various types of data to facilitate effective training management, documentation, and evaluation. In this study, SimCapture will be applied in the following ways: Each faculty member and student will be provided with a personal account, and the platform will group participants accordingly.

Faculty will develop digital assessment and evaluation tools for each nursing skill. During in-class rehearsal, instructors will annotate student performance using tablets on the cloud system, while students will record their own procedures on mobile devices and upload them to the cloud platform. Students will be able to view their group members' videos, along with instructor feedback, to learn from peers' strengths and correct errors, thereby improving learning outcomes. The platform will be accessible both in the simulation laboratory and remotely, enabling students to review, practice, and participate in asynchronous discussions without time or location restrictions. Students can document their learning progress, which enhances motivation, self-efficacy, and confidence in skill mastery. Faculty will be able to monitor student learning, respond to questions, and review learning histories to design individualized or remedial instructional plans.

(3) Monitoring the Intervention (Data Collection and Feedback)

Throughout the intervention, feedback data will be continuously collected (Table 3), including:

- Student learning portfolios
- SimCapture backend learning records
- Self-efficacy questionnaires
- Learning motivation questionnaires

These data will serve as the basis for reflection and revision of the action plan.

Additionally, trained teaching assistants (TAs) and part-time assistants will serve as observers to support the teaching process and document observations.

(4) Data Analysis, Reflection, and Adjustment of the Action Plan

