Students' technical performance will be assessed using OSCEs, administered twice per semester (midterm and final). Each OSCE will cover nursing skills taught during the course. The OSCE blueprint includes examinee guidelines, standardized patient instructions, examiner guidelines, scoring criteria, evaluation forms, equipment lists, and a demonstration video. The scoring rubric evaluates preparation, procedural performance, communication and caring expressions, health education content, and overall logical flow of operations. Exam content will be determined by the Clinical Nursing Skills teaching committee and validated by five clinical nursing experts and faculty members prior to implementation.

8. Data Analysis

(1) Quantitative Data

Questionnaire data will first be organized in Excel, and the accuracy of data entry will be verified. Preliminary descriptive statistics will be conducted using SPSS, followed by appropriate statistical analyses according to the nature of each research question. A significance level of $p < 0.05$ will be adopted to determine statistical significance. The corresponding research questions and statistical methods are summarized in Table 6.

Correspondence Between Research Questions and Statistical Methods

Research Question	Statistical Method
What are the differences in self-efficacy, learning motivation, and OSCE performance between the two groups at the first measurement?	Independent samples t -test
What are the trends in changes in self-efficacy between the two groups?	Generalized Estimating Equations (GEE)
What are the pre- and post-test changes in learning motivation and OSCE scores within each group?	Paired samples t -test
What are the post-test differences in learning motivation and OSCE scores between the two groups?	Independent samples t -test

(2) Qualitative Data

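### The paired pre/post t-test on OSCE scores appears to set the final against the midterm, although earlier finals ran 15.9 to 18.8 points below midterms without the intervention

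*Protocol*

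**What the plan says.** Section 8, Data Analysis, (1) Quantitative Data, lists four research questions with their methods. One reads "What are the pre- and post-test changes in learning motivation and OSCE scores within each group"; its method is a paired samples t-test, at a significance level of 0.05. Two other rows compare OSCE performance between two groups, at the first measurement and at post-test, by independent t-tests.

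Section 7, (3) OSCE Scores, says the exams are "administered twice per semester (midterm and final). Each OSCE will cover nursing skills taught during the course". It adds: "Exam content will be determined by the Clinical Nursing Skills teaching committee". Section 4.1 is consistent with one midterm and one final: "Two additional weeks are allocated for skills examinations". No OSCE before the course is described.

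On the intervention, section 6, (2), says: "The SimCapture teaching management platform will serve as the central tool for course delivery". Section 5 adds: "In the practical sessions, the SimCapture simulation-based training platform will be introduced to support course integration, management, and evaluation". Section 2 lists better OSCE scores as the first of three objectives.

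The only OSCE results given are in section 1, "Table 1. OSCE Performance in Clinical Nursing Skills I, 2019–2021 Academic Years".

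**The concern.** A paired t-test takes zero change as its null. That is a sensible reference only if pre-test and post-test measure the same thing on the same scale, and if the pre-test comes before the intervention. On the midterm-to-final reading neither condition is shown to hold.

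- **The exams are not described as equated.** A committee sets the content, and Table 1 shows a large drop from midterm to final in every year listed. Zero change was not the usual result without SimCapture.
- **The midterm is not shown to be an unexposed baseline.** SimCapture delivers the course, and no period without it before the midterm is described. Any benefit already present at the midterm is subtracted from the estimated change.

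The row would then mainly measure the difference between two exams. A real, moderate gain could be reported as a significant decline on an outcome named in the objectives.

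**Working it through.** **Inputs from the protocol (section 1, Table 1; section 5).** Midterm and final means were 70.4 and 52.6 (2019), 70.0 and 51.2 (2020), 68.2 and 52.3 (2021). There are about 85 students per year.

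**Reproducing Table 1.** The overall average is (midterm + final)/2: (70.4 + 52.6)/2 = 61.5; (70.0 + 51.2)/2 = 60.6; (68.2 + 52.3)/2 = 60.25. All three match the table.

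**Historical gap, final minus midterm.** 52.6 − 70.4 = −17.8; 51.2 − 70.0 = −18.8; 52.3 − 68.2 = −15.9. The mean is −17.5 and the SD of the three gaps is 1.473. The 95% prediction interval for a further year is −17.5 ± 4.303 × 1.473 × √(4/3), or −24.8 to −10.2. It rests on three yearly means, so it is only a rough guide.

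**Expected paired change.** This is the historical gap plus the relative gain, where relative gain means the gain on the final minus the gain on the midterm. If the gap stays within the observed range:

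| Relative gain | Expected change |
|---|---|
| 0 | −15.9 to −18.8 |
| 5 | −10.9 to −13.8 |
| 10 | −5.9 to −8.8 |
| 15 | −0.9 to −3.8 |

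This step needs no SD. The sign turns positive only above 15.9 to 18.8 points.

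**What the test would report.** The protocol gives no SD of the paired differences, so 10, 15 and 20 are assumed. A group is taken as one year cohort, n = 85, and the test as two-sided at 0.05. Power comes from the noncentral t distribution with noncentrality (gap + gain)/(SD/√n). For example, at the mean gap with gain 10 and SD 20 it is −7.5/(20/√85) = −3.46.

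Probability of a significant decline, n = 85:

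| Gap | True relative gain | SD 10 | SD 15 | SD 20 |
|---|---|---|---|---|
| −17.5 (mean) | 10 | >0.999 | 0.995 | 0.928 |
| −17.5 | 15 | 0.625 | 0.330 | 0.206 |
| −15.9 (smallest observed) | 10 | >0.999 | 0.948 | 0.767 |
| −15.9 | 15 | 0.127 | 0.079 | 0.061 |
| −10.2 (favourable prediction limit) | 5 | 0.997 | 0.883 | 0.656 |
| −10.2 | 10 | 0.036 | 0.032 | 0.030 |

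A simulation of 100,000 runs agreed at the settings checked (for example 0.926 at the mean gap, gain 10, SD 20).

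Probability of a significant improvement, n = 85:
- 10-point gain: below 0.001 at the mean and smallest observed gaps, and about 0.02 at −10.2.
- 15-point gain: at most 0.001 at the mean gap and at most 0.009 at −15.9, but 0.992, 0.833 and 0.593 (SD 10, 15, 20) at −10.2.

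**Thresholds at the mean gap.** The smallest significant change is t(0.975, 84 df) × SD/√85 = 2.16, 3.24 and 4.31 for SD 10, 15 and 20. The expected change is a significant decline for gains below 17.5 minus these values (15.3, 14.3, 13.2). It is a significant improvement for gains above 17.5 plus these values (19.7, 20.7, 21.8).

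**Smaller groups.** If a group is half a cohort (n = 43), a 10-point gain gives a significant decline with probability 0.998, 0.893 and 0.671 at the mean gap, and 0.966, 0.712 and 0.472 at −15.9.

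**The case against.** The strongest reply is that the row asks a neutral question about change, and a fall from midterm to final would be a correct answer to it. The protocol does not say that this row estimates the SimCapture effect, and an interval for the paired change carries the same information as the test. This does not dispose of the point. Improving OSCE scores is a stated objective, and calling the two exams pre-test and post-test treats the first as a baseline.

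The pairing is inferred, and this stands as a limit. The protocol never says which OSCE is pre and which is post. Another pairing is conceivable, though none is described. That the midterm is exposed is likewise inferred, because no start date for SimCapture relative to the midterm is given.

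The between-group post-test comparison is also planned. If both groups share the same gap, exam difficulty cancels there. That limits the damage to the study but does not repair the within-group test.

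The evidence is narrow, and this also stands. Table 1 covers Clinical Nursing Skills I in 2019 to 2021, whereas the study enrols "second- and third-year undergraduate nursing students in the 2024–2025 academic year" and includes Clinical Nursing Skills II, for which no scores are given. The probabilities depend on an assumed SD, group size and gap; for the same 10-point gain they run from 0.03 to above 0.99.

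**Conclusion.** The concern holds, conditionally, and should be fixed. If pre and post mean midterm and final, and a gap like the earlier ones persists, the expected paired change in Clinical Nursing Skills I is negative for any relative gain below 15.9 to 18.8 points. That result uses only Table 1 and the assumption of persistence. At the observed gaps a 10-point gain would usually be reported as a significant decline. A 15-point gain would almost never be reported as an improvement. Only a gain of roughly 20 to 22 points would be expected to reach significance in the right direction at the mean gap. A gap that shrank to about 10 points would remove most of the false declines at a 10-point gain. Nothing can be said about Clinical Nursing Skills II. Confidence is medium, because both the pairing and the persistence are assumptions.

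**What to change.** In sections 7 (3) and 8 (1), state which OSCE is the pre-test and which the post-test, and when SimCapture starts relative to each. If they are midterm and final:

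- remove OSCE from the paired pre/post row as a test of improvement;
- do not call the midterm a pre-test or baseline;
- report the midterm-to-final change descriptively, with mean, SD and interval, and do not read it as an effect of the intervention.

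This costs wording only.

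Optionally, where permission and records allow, compare like with like: the 2024–2025 midterm with earlier midterms and the final with earlier finals, or student-level change with that of earlier classes. This needs student-level records and rests on only three earlier classes sitting exams not shown to be constant. The analysis should carry the uncertainty of that historical reference, and the report should name the non-randomised comparison and possible exam differences as limitations.

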Qualitative data will be analyzed using content analysis. Learning portfolio records will be systematically coded and categorized, with each entry labeled by collection date and source (e.g., file, questionnaire, observation, or reflection). Students will be assigned identification codes in the format *S-n-*****. The principal investigator will first classify and organize the collected data, then repeatedly review and integrate the categorized materials. Data will be refined and regrouped into appropriate categories, with iterative reading and reclassification until the categories adequately represent distinct characteristics. This cyclical process ensures analytic rigor and reliability. To protect participants' rights, identifiable student learning records will not be directly presented, and particular care will be taken to avoid any breach of confidentiality or learning equity.

8. Ethical Considerations

Prior to study implementation, the research protocol will be submitted to and approved by the Institutional Review Board (IRB) of the study site. All data will be de-identified before analysis. Before participation, students will be fully informed of the purpose of the study and the evaluation procedures. They will be explicitly advised that participation is entirely voluntary, that they retain the absolute right to refuse to answer any question, and that they may withdraw from the study at any time without providing a reason. Students who withdraw will still complete written examinations, OSCEs, coursework, and self-directed learning sign-in records and will remain eligible to receive course credits. Students who agree to participate will be asked to provide written informed consent. All questionnaires will be collected

anonymously. Interview data will be kept strictly confidential, and all collected data will be coded to ensure participants' names are not disclosed. Hard-copy data will be stored in locked cabinets, while electronic data will be password-protected to prevent unauthorized access.

Reference

1. Lee K-C, Ho C-H, Yu C-C, Chao Y-F. The development of a six-station OSCE for evaluating the clinical competency of the student nurses before graduation: A validity and reliability analysis. *Nurse education today*. 2020;84:104247.
3. Lee K-C, Yu C-C, Hsieh P-L, Li C-c, Chao Y-FC. Situated teaching improves empathy learning of the students in a BSN program: A quasi-experimental study. *Nurse Education Today*. 2018;64:138-143.

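### Motivation and OSCE scores are tied to t-tests that cannot use incomplete pairs, although the protocol foresees attrition; one repeated-measures model per outcome would use every student

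*Protocol*

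**What the plan says.** Section 5 puts the study population at about 170, that is "about 85 students per year, with possible attrition due to withdrawal or leave of absence". It gives no attrition rate. The ethics section allows withdrawal at any time and refusal of any question. It adds: "Students who withdraw will still complete written examinations, OSCEs, coursework, and self-directed learning sign-in records". It does not say whether the OSCE scores of those students are analysed.

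The table of research questions and methods in Section 8 (Data Analysis) fixes a test for each question:

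- "What are the pre- and post-test changes in learning motivation and OSCE scores within each group": paired samples t-test.
- "What are the post-test differences in learning motivation and OSCE scores between the two groups": independent samples t-test.
- "What are the trends in changes in self-efficacy between the two groups": generalized estimating equations (GEE).

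Section 7 says that OSCEs are "administered twice per semester (midterm and final").

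**The concern.** A paired t-test uses only students with both scores. A post-test t-test uses only students with a post score, whether or not a first score exists. If the students who are lost differ from those who stay, each test describes a selected group, and the two rows can describe different students. The GEE row can keep a student with incomplete data. One table therefore treats the same incomplete student differently according to the outcome, and gives no reason.

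Selective loss is plausible here. Table 2 in Section 1 links poor OSCE performance with little practice, low interest and low self-confidence. The protocol does not say that such students will leave, but it gives no ground for assuming that loss is unrelated to scores.

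At stake is the size of the reported change in two of the three target outcomes. For the OSCE, part of the loss would also be avoidable, because students who leave the study but stay on the course still sit the exam.

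**Working it through.** **The plan's own figure.** 2 x 85 = 170, which agrees with Section 5. It is the size of two year cohorts. The protocol gives no effect size, SD, dropout rate or pre-post correlation to work from.

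**Assumptions, none from the protocol.** Scores in SD units; pre-post correlation r = 0.4 to 0.7; loss of 10% to 20%; log-odds of loss falling by 0.7 to 1.0 per SD of the first score.

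**Loss that depends on the first score.** Let D be the amount by which the mean first score of the remaining students exceeds that of all students. With normal scores:

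- bias in the remaining students' post-test mean = r x D
- bias in the paired change = r x D - D = -(1 - r) x D

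Numerical integration of the logistic loss model gives D = 0.067 at 10% loss with slope 0.7, and D = 0.173 at 20% loss with slope 1.0. The extremes are then:

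| Quantity | Smallest | Largest |
|---|---|---|
| Paired change | -(1 - 0.7) x 0.067 = -0.02 | -(1 - 0.4) x 0.173 = -0.10 |
| Remaining students' post-test mean | 0.4 x 0.067 = +0.03 | 0.7 x 0.173 = +0.12 |

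The shift is additive, so it applies whether the true change is a rise or a fall. A likelihood-based repeated-measures analysis of the same data has a change bias of about 0.00.

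**Other mechanisms.** Simulation with r = 0.5, 10% loss and a steeper slope of 1.5:

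| Loss depends on | Paired change | Post-test difference, loss in one group only | Post-test difference, equal loss in both |
|---|---|---|---|
| low first score | -0.06 | +0.06 | 0.00 |
| low post score | +0.06 | +0.12 | 0.00 |
| low change | +0.12 | +0.06 | 0.00 |
| nothing | 0.00 | 0.00 | 0.00 |

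The signs are opposite in the first row only. When both groups lose students alike, the post-test difference is unbiased under every mechanism.

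**Limit of the alternative.** When loss depends on the post score (r = 0.5, 10% loss, slope 1.0), the likelihood model's change bias is about +0.07, against +0.05 for complete pairs. At r = 0.4, 20% loss and slope 1.0 it reaches about +0.15, against +0.10.

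**Scale.** With 85 students in a group, the standard error of a paired change is sqrt(2(1 - r)/85): 0.12 at r = 0.4 and 0.08 at r = 0.7. At r = 0.4 the largest paired bias is 0.10/0.12, or about 0.8 of a standard error.

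**The case against.** The strongest case against is that this belongs in a statistical analysis plan, that attrition is called only possible, and that the biases are below one standard error. The courses are mandatory and withdrawn students still sit the OSCEs, so heavy score-related loss of OSCE data has no support in the text. Much of this stands. The absence of a missing-data rule or analysis set is no finding, and the rate and mechanism used above are assumptions. What does not fall away is that the protocol names the tests, and the tests it names cannot use incomplete pairs.

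Three stronger readings are tempting and are not supported:

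- **Selective dropout biases the two tests in opposite directions.** This is not general. It needs loss that depends on a low first score, and for the post-test comparison also unequal loss between groups. The protocol supports no particular mechanism.
- **The plan discards OSCE scores of withdrawn students.** The text leaves their use open. It may depend on consent, and the consent pages are not in the copy reviewed.
- **A mixed model cures the problem.** It does so under missing-at-random. If loss depends on the unseen post score, its change bias can exceed that of complete pairs.

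Two further objections stand as limits on any remedy. The ethics section calls the questionnaires anonymous, though it also says that data are coded. Without a linking code, neither the planned paired test nor a mixed model is possible for motivation. And if pre and post mean midterm and final, Table 1 shows finals below midterms by 17.8 (70.4 - 52.6), 18.8 (70.0 - 51.2) and 15.9 (68.2 - 52.3) points in 2019, 2020 and 2021. No model makes two different exams comparable.

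**Conclusion.** The concern holds in limited form. The protocol foresees possible attrition, yet it fixes paired and post-test t-tests for motivation and OSCE that leave out part of the observed data, and reserves a repeated-measures method for self-efficacy. Under loss related to a low first score, the paired change is biased by about -0.02 to -0.10 SD and the remaining students' post-test mean by about +0.03 to +0.12 SD. These figures rest on the assumed 10-20% loss, slopes of 0.7 to 1.0 and correlation of 0.4-0.7. The between-group post-test difference is affected only if loss differs between groups. The effect is modest. The change is worth making because it is cheap, not because the planned tests are certain to mislead. Silence on withdrawn students' OSCE scores is a separate gap that one sentence closes.

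**What to change.** 1. Replace the paired and post-test t-test rows for motivation and OSCE with one repeated-measures linear mixed model per outcome: REML, with time, group and group-by-time, on all students with at least one score. Read the within-group changes and the post-test group difference from it as contrasts, so both questions in the table are still answered.
2. State that questionnaires are linked across occasions by a study code that carries no name, and reconcile this with the statement that they are anonymous.
3. State that OSCE scores of students who withdraw from the study but still sit the exam stay in the analysis where consent allows, and ask for that consent in one sentence. For these students this removes the missing OSCE scores whatever the reason for leaving. It does not help for students on leave of absence.

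The cost is two table rows, a line on linkage and a consent sentence; SPSS, the package already named, can fit the model. The downsides are slightly more analysis work and reliance on missing-at-random, so loss that depends on the unseen post score remains uncorrected.
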